**Withdrawal Criteria.**

Patients meeting these intra-operative and post-operative criteria will be withdrawn from the study because of the likelihood that these characteristics will independently affect primary and secondary study outcomes. However, primary and secondary outcomes will still be collected for these patients and results included in an “intention-to-treat” analysis.

- Post-operative intubation longer than 16 hours.
- Cardiopulmonary bypass time  $> 3$  hours or aortic cross-clamp time  $> 120$  minutes.
- Return to OR during hospital admission.

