### Post-operative pain control

Patients will be treated with fentanyl boluses during the immediate post-operative period and while intubated

in the ICU, until they are able to use the PCA. Pain will be evaluated using the adult NVPS (see Appendix II) and medication will be administered for NVPS score  $\geq 4$ . Per routine cardiovascular ICU protocol, patients will receive Indomethacin 25 mg every 8 hours for three doses if they meet the following criteria: (1) Cr  $< 1.5$  and (2) age  $< 75$ .

The patients will be extubated per the standard cardiovascular ICU protocol (see Appendix IV). Following extubation, pain will be assessed using the NRS (see Appendix II) and pain regimen will be adjusted for NRS score  $\geq 4$ . All patients will receive either fentanyl IV or hydromorphone IV (if fentanyl is poorly tolerated or patient is allergic to fentanyl) via PCA device following extubation. The PCA will be continued for the first 48 hrs postoperatively.

The initial PCA orders will be written by a study team member. If the PCA requires dose adjustment or medication change, then the cardiovascular ICU or floor providers will modify the order per the protocol below. This is a safety mechanism, in case a study team member is unavailable at the time.

The PCA will be set accordingly (see Appendix V):

- A fentanyl PCA will be set up with the following specifications:
  - Loading dose: 1 mcg/kg IV bolus fentanyl divided into 2 doses given 10 minutes apart
  - Bolus dose: 10 mcg IV bolus fentanyl with a lockout interval of 15 minutes and maximum 1 hr limit of 80 mcg. The incremental bolus dose of fentanyl will be increased by 25-50% if analgesia is inadequate (NRS  $\geq 4$ ).
  - If the patient experiences undue side effects from fentanyl PCA (see below) and pain is still inadequately controlled at current dosage, then the patient will be switched over to a dilaudid PCA. However, if pain is controlled with the fentanyl PCA bolus, but the patient is experiencing undue side effects, then the following steps will be taken:
    1. Decrease the PCA bolus dose to 7.5 mcg IV bolus with a lockout interval of 15 minutes.
    2. If the patient still does not tolerate the fentanyl PCA well, then decrease the PCA bolus dose to 5.5 mcg IV bolus with a lockout interval of 15 minutes.
    3. If the patient still does not tolerate the fentanyl PCA well, then decrease the PCA bolus dose to 4.0 mcg IV bolus with a lockout interval of 15 minutes.

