    4. If patient continues to not tolerate the fentanyl PCA well, then switch over to a dilaudid PCA.
- If the patient is allergic to fentanyl or continues to poorly tolerate fentanyl (despite dose adjustments), then the patient will be switched over to a dilaudid PCA:
  - Loading dose = 0.02 mg/kg IV bolus hydromorphone divided into 2 doses given 10 minutes apart,
  - Bolus dose = 0.2 mg IV bolus hydromorphone with a lockout interval of 15 minutes and maximum 1 hr limit of 1.6 mg. The incremental bolus dose of hydromorphone will be increased by 25-50% if analgesia is inadequate (NRS  $\geq 4$ ).
- “Poor tolerance” and/or undue side effects of the narcotic may include:
  - Excessive nausea/vomiting refractory to antiemetics.
  - Itching/rash deemed related to narcotic and refractory to Benadryl.
  - Altered mental status or feeling “high” from narcotic bolus.
- The PCA dose may be titrated up or down to attain adequate anesthesia and minimize side effects from the narcotics.
- Naloxone may be used for respiratory depression (respiratory rate  $< 8$  breaths per minute), over-sedation or muscle rigidity secondary to opioid overdose. The PCA bolus dose will be decreased by 25-50% if this occurs.

Following discontinuation of the PCA, patients will be transitioned to Percocet 5/325 mg 1-2 tabs PO every 4 hours as needed or Hydrocodone-Acetaminophen 5/325 mg 1-2 tabs PO every 6 hours as needed.

Rescue pain medication:

- A dose of Toradol 15 mg IV or Tramadol 50-100 mg PO will be administered as rescue medication if patient is still reporting inadequate analgesia ( $NRS \geq 4$ ), but has already met the 1 hour maximum dose of fentanyl or dilaudid.
- Once the patient has been transitioned to PO pain medications, a dose of dilaudid 0.5 mg IV or morphine 2 mg IV may be administered as rescue medication if the patient is still reporting inadequate analgesia ( $NRS \geq 4$ ), but cannot receive additional narcotics (i.e. Percocet or Hydrocodone-Acetaminophen) for that time period.

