### **Measurements/Data collection.**

#### Pain assessment:

The adult NVPS will be used to assess pain while patient is intubated in the ICU. This scale is used routinely in intubated and nonverbal critically ill patients in the Cardiovascular ICU (CVICU). The NVPS will be performed by a blinded care provider (e.g. nurse or nurse manager) who is trained on how to use the scale. Time 0 will be designated as the time the patient leaves the OR. The NVPS will be performed every 2 hrs for the first 4 hrs and then every 4 hrs following until the patient is extubated.

The numerical rating scale (NRS) ranging from 0 (no pain) to 10 (worst pain ever) will be used to assess pain

once the patient is extubated and alert. The scale will be administered every 4 hrs for the first 72 hrs post-op.

Cumulate pain scores at time points at 2, 4, 8, 12, 24, 36, 48, 60 and 72 hrs will be compared.

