#### Adverse events will be recorded:

- Adverse cardiac events: angina, myocardial infarction, new cardiac arrhythmia
- Neurologic: transient ischemic attack (TIA), stroke (CVA)
- Gastrointestinal: constipation, ileus, bowel obstruction
- Pulmonary: Pneumonia
- Renal: renal insufficiency
- Wound infection, wound dehiscence

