**Table 2: Study Schedule and Procedures (Cont.)**

Procedure	After Study Drug Administration														
	2-72 Hours														Site Visit
	Time post-drug				0	2	4	8	12	24	36	48	60	72	
	Study Day	Day -30 to -1	Day -1 to 1	1	1	1	1	1	1	2	2	3	3	4	30
	Time Window (±h)					0.25	0.25	0.5	0.5	1	2	2	4	4	96
Oral narcotics												X	X		
Subject's satisfaction with postoperative analgesia									X				X	X	
Brief Pain Inventory	X													X	
Record occurrence and duration of nausea/vomiting					X	X	X	X	X	X	X	X	X	X	
Record date/time of each bowel movement					X	X	X	X	X	X	X	X	X	X	
Record date/time of each rescue pain medication dose					X	X	X	X	X	X	X	X	X	X	
Subject productivity (date subject returned to work or normal daily activities)														X	
Concomitant medications 	X	X	X	X	X	X	X	X	X	X	X	X	X	X	
Record AEs and SAEs					X	X	X	X	X	X	X	X	X	X	

 Clinical labs will include Complete Metabolic Panel, CBC and INR/PTT.

 Temperature, heart rate, blood pressure, oxygen saturation will be monitored continuously in the cardiovascular ICU (CVICU) and at the time points listed.

 Inspiratory capacity (IC) will be measured using the handheld spirometer at baseline (pre-op) and then once between POD #1-2.

 Pain will be assessed with the NVPS or NRS scores at the end of anesthetic and before the first dose of rescue pain medication.

 Pain will be assessed with NVPS if the patient is still intubated and/or sedated. Pain will be assessed with the NRS score if the patient is extubated and alert/responsive.

 All medications that the subject used within 3 days prior to surgery will be recorded; including medication name, dose and date last taken.

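### The Toradol rescue order has no age or creatinine condition, although the same section withholds indomethacin on both; it should say when Tramadol is used instead

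*Combined protocol and SAP*

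**What the plan says.** Two orders in the section on post-operative pain control matter here.

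- **Indomethacin.** Under the unit's routine protocol, patients receive "Indomethacin 25 mg every 8 hours for three doses if they meet the following criteria": creatinine below 1.5 and age below 75.
- **First rescue line.** "A dose of Toradol 15 mg IV or Tramadol 50-100 mg PO will be administered as rescue medication" if the patient still reports NRS 4 or more, "but has already met the 1 hour maximum dose of fentanyl or dilaudid". These are its only two conditions. The line joins the drugs with a plain alternative and gives no rule for choosing.

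Elsewhere in the protocol:

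- Entry requires age 18 or over and sets no upper limit (Age of Subjects; Inclusion Criteria).
- Pre-operative creatinine of 1.5 mg/dL or more excludes the patient (Exclusion Criteria).
- The adverse-event list includes "Renal: renal insufficiency".
- Data Analysis lists Toradol and Tramadol as examples of breakthrough medication, under opioid requirement.

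**The concern.** The protocol writes out two patient characteristics that make indomethacin unsuitable, then directs another drug of the same class without mentioning either. That Toradol and indomethacin are both NSAIDs is general pharmacology; the documents do not say so.

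Staff following the written order could give Toradol to the very patients from whom the protocol withholds indomethacin. The order does contain a non-NSAID alternative, but nothing tells staff when to prefer it. Tramadol is also oral, and the bowel-regimen section recognises a period before patients tolerate oral drugs. In that period Toradol is the only drug in the order that can be given.

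**Working it through.** The plan states no figure on this point, so the check is a comparison of text, with one calculation to see whether the order can come into play.

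**Step 1. The two orders side by side**

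| | Indomethacin | Toradol (first rescue line) |
|---|---|---|
| Age | below 75 | no condition |
| Creatinine | below 1.5 | no condition |
| Given when | scheduled | NRS 4 or more and hourly PCA maximum met |
| Alternative | none named | Tramadol, with no rule for choosing it |

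**Step 2. Which enrolled patients fall in the gap**

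- *Age 75 or over.* Eligible, refused indomethacin, allowed Toradol. No entry criterion closes this gap.
- *Under 75, creatinine 1.5 mg/dL or more after surgery.* Refused indomethacin, allowed Toradol. The indomethacin order does not say which creatinine value it means and gives no unit; mg/dL is taken from the exclusion criterion. Because a pre-operative value at that level already excludes, the indomethacin criterion can only matter for a post-operative rise.
- *Under 75, creatinine below 1.5.* Both drugs allowed, so the two orders agree on these criteria.

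**Step 3. Can the rescue order be reached?**

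Inputs are the PCA settings in the same section: 10 mcg fentanyl bolus, 15-minute lockout, 80 mcg hourly limit, bolus increases of 25-50%.

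- Boluses per hour: 60 / 15 = 4.
- Starting maximum: 4 x 10 = 40 mcg/h, half the limit.
- Bolus needed to reach the limit: 80 / 4 = 20 mcg.
- With 50% increases: 10, 15, 22.5 mcg. The second increase gives 4 x 22.5 = 90 mcg/h of demand, above 80.
- With 25% increases: 10, 12.5, 15.6, 19.5, 24.4 mcg. The third gives 78.1 mcg/h, just short; the fourth gives 97.7 mcg/h.
- Hydromorphone: 4 x 0.2 = 0.8 mg/h against 1.6 mg, the same ratio.

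The limit therefore cannot be met on boluses at the starting setting. The protocol's own titration reaches it after two to four increases. It could come sooner if the loading dose counts toward the limit, which is not stated: at 80 kg, 1 mcg/kg is 80 mcg. So the order is reachable, but these numbers do not say how often it will be used.

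**Step 4. How long the order applies**

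It is tied to the PCA, which runs for the first 48 hours. After the change to oral drugs the rescue is dilaudid or morphine, and the gap no longer arises.

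**The case against.** The strongest objection is that the gap may be closed outside the visible text. The indomethacin criteria are described as routine unit protocol, and the unit may have a similar rule for Toradol. The section also points to Appendix V for PCA set-up, and that flow chart is not shown. This stands as a limit on the finding. It carries less weight than it might, because the risk section says PCA is not routine after cardiac surgery. The rescue line is therefore a study-specific pathway, and the body text should be complete on its own.

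Safety oversight is a second answer: the Clinical Monitor reviews adverse events as they occur, and the independent monitor reviews them unblinded. Both act after exposure and do not guide the choice of drug.

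A reader might also infer that Toradol must not overlap with indomethacin, or that the three doses at 8-hour intervals are a cap that Toradol should share. The documents do not support either. Three doses is the length of a scheduled indomethacin course, not a stated safety ceiling. Table 2 has the row "Record date/time of each rescue pain medication dose", so repeat doses are foreseen, but that row also covers the later opioid rescue line and sets no limit.

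An 8-hour gap would also do harm. If indomethacin is given at 0, 8 and 16 hours (start time assumed), Toradol would be barred until 16 + 8 = 24 hours in everyone receiving it. With patients aged 75 or over barred as well, nearly the whole trial would lose its only IV drug in this rescue line for about the first day.

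**Conclusion.** The point holds as a cheap improvement for patient safety. On the visible text, patients refused indomethacin for age, or for a post-operative rise in creatinine, can receive Toradol. The age part is the clearer of the two; the creatinine part is narrow because of the entry exclusion.

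The number of patients affected is not estimated: the documents give no age distribution, no rate of post-operative creatinine rise and no rate of rescue use. A reader might want a total Toradol exposure or an hours-of-overlap figure. The order states no interval between rescue doses, so any such figure would come from the interval assumed and not from the plan.

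Nor do the documents support reading this as a threat to the primary outcomes, sample size or power. The same order applies in both arms, and nothing in the power calculation depends on it.

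The conclusion assumes that the two drugs share a class, that the indomethacin creatinine limit is in mg/dL, and that neither the Appendix V chart nor a unit rule already supplies the conditions.

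**What to change.** Reword the first rescue line along these lines: *Toradol 15 mg IV only if age is below 75 and the most recent available creatinine is below 1.5 mg/dL; otherwise Tramadol 50-100 mg PO, or call the ICU or floor provider if the patient cannot take PO.* Both thresholds are the protocol's own. If the Appendix V chart shows rescue drugs, make it match.

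Ask the study pharmacist to decide whether Toradol may be given during the indomethacin course and to set a repeat-dose limit. The documents give no basis for choosing either figure here.

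No new test is needed. Table 2 schedules study labs only at screening (its footnote reads "Clinical labs will include Complete Metabolic Panel, CBC and INR/PTT"), so a post-operative rise will be seen only if routine care has measured it. That is why the wording says most recent available.

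The costs are:

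- **Somewhat more Tramadol use.** Appendix VI has no Tramadol conversion, while the opioid section converts all narcotics to fentanyl equivalents. Tramadol should stay reported as breakthrough medication, as Data Analysis has it.
- **A provider call, and some delay,** for restricted patients who cannot yet take oral drugs.

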### Standardized bowel regimen

Bowel regimens will be standardized to control for differences in prescribed stool softeners and laxatives.

All patients will receive Colace 1 tab twice daily, Dulcolax 1 tab oral every morning and Senna 1 tab nightly once they are able to tolerate PO medications. If patients do not have a bowel movement by post-operative day 2 (POD #2), the bowel regimen will be increased until the patient has a bowel movement. The order of escalation of prescribed medications will be as follows:

- POD #2 AM: Dulcolax suppository + Milk of Magnesia
- POD #2 PM: Lactulose oral or Miralax
- POD #3 AM: Lactulose oral or Miralax (whichever he/she did not receive on POD #2)
- POD #3 PM: Enema (soapsuds, fleets, mineral oil, etc.)

### Follow-up

The subjects will be seen by their primary care physician within 7-10 days per standard URMC protocol. They will return to clinic for a post-operative visit approximately 30 days from discharge. During this visit, they will be administered a brief questionnaire regarding presence/quality of continued pain following discharge (BPI-SF, see Appendix III). They will also be asked to rate the quality of their pain control during their hospitalization and recall their time to return to work or daily activities. During this visit, they will also be debriefed about the study.

In addition, in order to assess the success of maintenance of the blind, we will ask the subjects to: (1) guess which treatment (Exparel® or placebo) they think they received in the study, (2) express their degree of certainty regarding their guess, and (3) explain their reasons for their guess.

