### Parasternal intercostal nerve block

The parasternal blocks will be performed by a blinded surgeon at the end of surgery, just prior to sternal closure.

The medication will be prepared and dispersed by the study pharmacist in a concealed vial. The contents of the vial will be drawn up into two sheathed sterile 30 cc syringes by the operating room staff. Due to the distinct visual characteristics of normal saline (transparent) compared to Exparel® (translucent), sheathed syringes will be used to maintain blinding of the surgeon and operating room staff.

The components of a parasternal nerve block include anesthetizing the anterior cutaneous branches of intercostal nerves two through six and the deep subcutaneous layers around the mediastinal drain sites (Fig. 2). First, sequential intercostal blocks will be performed with 4 mL per intercostal space across 5 intercostal spaces bilaterally. Then 10 mL will be injected in the superficial to deep subcutaneous tissue surrounding mediastinal drains. A total of 50 mL of either 0.9% normal saline or 50 mL of 0.53% Exparel® will be used for the parasternal block.

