#### Assessment of the blind

Subject responses at follow-up regarding speculation about the treatments received will be compared to each subjects actual group assignment in order to determine adequacy of the blind.

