### **Data Analysis.**

#### Data Analysis

- Patient demographics/Pre-op characteristics:
  - Age, sex, race, Body surface area (BSA)/BMI
  - Co-morbid diseases: Diabetes mellitus, COPD, smoking, hypertension, coronary artery disease
  - Left ventricular ejection fraction (%)

- Creatinine (Cr), Cr clearance
- Functional status: New York Heart Association (NYHA) class, American Society of Anesthesiologists (ASA) classification
- Intra-operative characteristics:
  - Operation type: CABG (on/off bypass), AVR, MV repair/replacement, Maze, Other (i.e. TV repair/replacement, ASD closure)
  - Internal mammary artery (IMA) harvested (one or two)
  - Cardiopulmonary bypass time (min)
  - Aortic cross-clamp time (min)
  - Intraoperative fentanyl ( $\mu\text{g}$ ), intraoperative versed (mg)
- Pain assessment:
  - Calculate mean area under the curve (AUC) for adult NVPS scores over the time intervals “0-2”, “0-4”, “0-8” and “0-12” hours.
  - Calculate mean AUC for NRS scores over the time intervals “0-12”, “0-24”, “0-36”, “0-48”, “0-60” and “0-72” hours.
- Opioid requirement:
  - Calculate mean cumulative fentanyl equivalent use for time intervals “0-2”, “0-4”, “0-8”, “0-12”, “0-24”, “0-36”, “0-48”, “0-60” and “0-72” hours.
  - Use of breakthrough pain medication (e.g. Toradol or Tramadol)
- ICU length of stay:
  - Calculate mean lengths of stay (hours) for placebo and Exparel® groups.
- Hospital length of stay:
  - Calculate mean lengths of stay (days) for placebo and Exparel® groups.
- Time to extubation:
  - Calculate mean time to extubation (hours) for placebo and Exparel® groups.
- Time to return of bowel function:
  - Calculate mean time to return of bowel function for placebo and Exparel® groups.
- Splinting
  - Mean change in IC from pre-operative to POD #1-2 in both treatment arms.
- Assessment of blind
  - Calculate the percentage of correctly guessed treatment assignments.

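### The pooled percentage of correct patient guesses, taken about 30 days after discharge, cannot separate a working drug from a failed blind

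*Combined protocol and SAP*

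**What the plan says.** All references are to the combined protocol and SAP.

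- **Timing (Follow-up).** "They will return to clinic for a post-operative visit approximately 30 days from discharge". The Debriefing Procedures section dates the visit from surgery instead; the difference does not affect this point.
- **What is asked (Follow-up).** The protocol states that "in order to assess the success of maintenance of the blind, we will ask the subjects to" guess between Exparel and placebo. The remaining items are "2) express their degree of certainty regarding their guess, and (3) explain their reasons for their guess".
- **What else happens at that visit (Follow-up).** "They will also be asked to rate the quality of their pain control during their hospitalization".
- **Purpose (Assessment of the blind).** The guesses "will be compared to each subjects actual group assignment in order to determine adequacy of the blind".
- **Analysis (Data Analysis).** "Calculate the percentage of correctly guessed treatment assignments". Nothing further is listed: no threshold, reference value, test, result by arm, or use of the certainty and reason items.
- **Staff.** Randomization and Blinding says that the surgeon, operating room staff and ICU and floor staff stay blinded. The nerve block section explains the sheathed syringes: "Due to the distinct visual characteristics of normal saline (transparent) compared to" the liposomal product. No guess is requested from any staff member.

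**The concern.** A guess can beat chance for two quite different reasons. The patient may have learned the allocation, which is a failure of blinding. Or the patient may have had little pain, inferred active drug and been right because the drug works, which is not. The second route is open here because the question comes long after the outcome window, and at a visit where patients are also asked to look back on their pain control. A single pooled percentage adds the two routes together.

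The outcomes make this matter. Pain is self-rated once the patient is extubated, and opioid use then comes largely through patient-controlled analgesia, so a positive result leans on the blind for its credibility. A check that drifts towards an unfavourable answer as the drug works better could cast doubt on a valid result, and it would not identify a real leak either.

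**Working it through.** **1. The plan's own figures.** The documents give no figure for the blinding check. The illustration borrows the inputs in Number of subjects, so I first confirmed that they reproduce the stated power. Inputs: control pain mean 53.2, SD 24.1; a 30% reduction, with the SD reduced accordingly; two-sided alpha 0.025; 39 per arm, about 37 after 5% dropout.

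- Treated mean = 0.7 × 53.2 = 37.24; treated SD = 0.7 × 24.1 = 16.87; difference = 15.96.
- SE at 37 per arm = √[(24.1² + 16.87²)/37] = 4.84. Power = Φ(15.96/4.84 − 2.24) = 85.5%. At 39 per arm it is 87.4%. The plan states 86%.
- The same steps for opioid use (23.2 mg, SD 8.3 mg) give 97.4% and 98.0%. The plan states 98%.

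The inputs are understood correctly.

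**2. Percentage correct under a perfect blind (assumed model).** Let pain be normal in each arm with these values, and let a patient guess Exparel when their pain falls below a cut c.

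Accuracy(c) = ½[Φ((c − 37.24)/16.87) + 1 − Φ((c − 53.2)/24.1)]

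The maximum is at c ≈ 51.5: ½[Φ(0.845) + 1 − Φ(−0.071)] = ½[0.801 + 0.528] = 66.5%. At the midpoint of the two means (45.22) it is 65.6%. Guessing from opioid use gives 69.9% at its best cut and 69.4% at the midpoint. With no drug effect it is 50%.

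**3. Why the metric cannot discriminate.** If the drug did nothing and a share L of patients knew their allocation while the rest tossed a coin, the percentage correct would be 50% + L/2. Setting this to 66.5% gives L = 33%. So a fully effective drug with no leak, and a useless drug with one third of patients unblinded, produce the same number.

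**4. How often it might be misread (assumed test).** The documents specify no test. Suppose a reader applies an exact two-sided 5% binomial test against 50% with 78 answers. P(X ≥ 49) = 0.015 and P(X ≥ 48) = 0.027, so the upper limit is 49 correct (63%). If a share q guess from pain and the rest toss a coin, the probability correct is 0.5 + 0.165q.

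| Share guessing from pain | Probability correct | Chance of 49 or more of 78 |
|---|---|---|
| 25% | 54.1% | 8% |
| 50% | 58.2% | 24% |
| 75% | 62.3% | 52% |
| 100% | 66.5% | 79% |

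With 74 answers (limit 46) the chances are 10%, 29%, 56% and 82%.

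**5. Imperfect recall (further assumption).** Let remembered pain equal actual pain plus independent error, with control-arm correlation r, and re-optimise the cut. If all patients guess from pain, accuracy falls to 60% at r = 0.7 and 57% at r = 0.5, and the chance of reaching 49 falls to 36% and 18%. If only half do, the chance is 10% and 6%.

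**The case against.** **No rule is breached.** A reader might infer that the plan would declare the blind broken whenever the drug works. The documents do not support that. They only call for a percentage to be calculated; the 50% reference, the 5% test and the guess model are all mine. The top figure of 79% further needs every patient to answer, to guess only from pain, to remember it accurately and to use the cut that best separates the arms, although each patient saw only one treatment. This objection stands: the finding is that misreading could happen, not that it would.

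**The useful data are already collected.** Certainty and reasons are asked for expressly to assess the blind. This also stands, and it narrows the gap to an analysis that is not specified. It does not close the gap, because the only listed analysis ignores both items.

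**Late timing can be defended.** Asking patients during the 72 hours could prompt speculation while they are rating their own pain. I accept this and do not propose moving the patient question.

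**The blind is protected where the products differ.** A reader might infer from their different appearance that allocation leaks in the operating room. The nerve block section provides a concealed vial and sheathed syringes for exactly this risk, and operating room staff are not assigned to rate any outcome. That the safeguard is untested is not evidence that it fails.

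**Conclusion.** The concern holds in this limited form: the stated metric confounds efficacy with unblinding, so it cannot do the job that the Assessment of the blind section gives it. That conclusion needs only the timing of the question and the single pooled percentage, both of which are in the text. The size is illustrative. It rests on normally distributed outcomes, the protocol's own 30% effect, an unknown share of patients guessing from outcome and an assumed test; across those shares the pain model runs from about 8% to 79%, and imperfect recall pulls it down.

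The check is supportive. Nothing here alters the primary analysis, the sample size or the conduct of treatment. I would class it as a cheap improvement.

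**What to change.** Amend Assessment of the blind and the matching line in Data Analysis as follows.

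1. Do not judge the blind on the pooled percentage.
2. Report guesses by arm, with 'don't know' allowed as an answer.
3. Cross-tabulate them by the certainty and stated reason already collected at follow-up. Interpret guesses attributed to pain relief separately from those attributed to anything else. A table by arm is not enough by itself, because efficacy shifts both arms; the reasons carry the distinction.
4. State that reasons are only indicative: a patient who learned the allocation may still cite pain relief.

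Optionally, add a one-line guess and reason from the surgeon or operating room staff straight after the injection. No outcome exists at that point, so efficacy cannot influence the answer. I would not add a bedside nurse's guess at 24 hours: it would follow a day of observed pain and opioid use, carry the same confounding, and fall inside the outcome window among staff who adjust analgesia.

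The cost is one added response option and a small extra tabulation. The optional staff question may draw some attention to allocation.
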